PRX - LAMA (except tiotropium) inhalers; n (%)	79 (0.4%)	129 (0.7%)	-0.0406	104 (0.3%)	160 (0.5%)	-0.0317	183 (0.4%)	289 (0.6%)	-0.028
PRX - ICS only inhalers; n (%)	2,225 (12.3%)	2,173 (12.1%)	0.0061	5,212 (16.7%)	5,163 (16.6%)	0.0027	7,437 (15.1%)	7,336 (14.9%)	0.006
PRX - LABA/LAMA inhaler use ; n (%)	114 (0.6%)	80 (0.4%)	0.0284	56 (0.2%)	42 (0.1%)	0.0258	170 (0.3%)	122 (0.2%)	0.020
PRX - Other LABA/ICS combination ; n (%)	916 (5.1%)	892 (5.0%)	0.0046	1,495 (4.8%)	1,469 (4.7%)	0.0047	2,411 (4.9%)	2,361 (4.8%)	0.005
PRX - COPD Maintenance therapy inhalers; n (%)	1,183 (6.6%)	1,169 (6.5%)	0.0040	1,729 (5.6%)	1,698 (5.5%)	0.0044	2,912 (5.9%)	2,867 (5.8%)	0.004
PRX - SAMA inhaler use; n (%)	656 (3.6%)	654 (3.6%)	0.0000	1,405 (4.5%)	1,431 (4.6%)	-0.0048	2,061 (4.2%)	2,085 (4.2%)	0.000
PRX - SABA use; n (%)	8,121 (45.1%)	8,083 (44.9%)	0.0040	13,827 (44.4%)	13,671 (43.9%)	0.0101	21,948 (44.7%)	21,754 (44.3%)	0.008
PRX - SABA/SAMA use; n (%)	2,035 (11.3%)	2,140 (11.9%)	-0.0187	4,133 (13.3%)	4,220 (13.6%)	-0.0088	6,168 (12.6%)	6,360 (12.9%)	-0.009
PRX - Antibiotics treatment (180 days to 31 days before CED); n (%)	6,629 (36.8%)	6,636 (36.8%)	0.0000	12,467 (40.1%)	12,337 (39.6%)	0.0102	19,096 (38.9%)	18,973 (38.6%)	0.006
PRX - Antibiotics treatment (30 days to CED); n (%)	2,690 (14.9%)	2,627 (14.6%)	0.0085	5,514 (17.7%)	5,441 (17.5%)	0.0053	8,204 (16.7%)	8,068 (16.4%)	0.008
PRX - Systemic Corticosteroids (with CPT) use (180 to 31 days before CED); n (%)	5,612 (31.1%)	5,577 (31.0%)	0.0022	9,580 (30.8%)	9,597 (30.8%)	0.0000	15,192 (30.9%)	15,174 (30.9%)	0.000

PRX - Systemic Corticosteroids (with CPT) use (30 days to CED); n (%)	1,016 (5.6%)	940 (5.2%)	0.0177	2,352 (7.6%)	2,284 (7.3%)	0.0114	3,368 (6.9%)	3,224 (6.6%)	0.012
PRX - Roflumilast; n (%) *	40 (0.2%)	31 (0.2%)	0.0000	102 (0.3%)	53 (0.2%)	0.0200	142 (0.3%)	084 (0.2%)	0.020
CVD the stable and the (Ather 197)	400 (2 00)	464 (2.69()	0.0000	FOC (4.00()	500 (4.00/)	0.0000	1,064 (2.2%)	1,062 (2.2%)	0.000
CVD - Unstable angina/MI; n (%) CVD - Stable Angina : n (%)	468 (2.6%) 318 (1.8%)	464 (2.6%) 314 (1.7%)	0.0000	596 (1.9%) 482 (1.5%)	598 (1.9%) 476 (1.5%)	0.0000	800 (1.6%)	790 (1.6%)	0.000
CVD - Any Heart failure (HF); n (%)	1,108 (6.1%)	1,131 (6.3%)	-0.0083	1,797 (5.8%)	1,807 (5.8%)	0.0000	2,905 (5.9%)	2,938 (6.0%)	-0.004
CVD - Atrial fibrillation; n (%)	911 (5.1%)	911 (5.1%)	0.0000	1,480 (4.8%)	1,488 (4.8%)	0.0000	2,391 (4.9%)	2,399 (4.9%)	0.000
CVD - Other dysrythmias ; n (%)*	1,256 (7.0%)	1,324 (7.3%)	-0.0116	1,788 (5.7%)	1,841 (5.9%)	-0.0086	3,044 (6.2%)	3,165 (6.4%)	-0.008
CVD - Valve disorder ; n (%)	231 (1.3%)	232 (1.3%)	0.0000	289 (0.9%)	283 (0.9%)	0.0000	520 (1.1%)	515 (1.0%)	0.010
CVD - Implantable cardioverter defibrillator ; n (%)*	51 (0.3%)	59 (0.3%)	0.0000	94 (0.3%)	67 (0.2%)	0.0200	145 (0.3%)	126 (0.3%)	0.000
CVD - CABG/PCI; n (%)	407 (2.3%)	400 (2.2%)	0.0067	375 (1.2%)	359 (1.2%)	0.0000	782 (1.6%)	759 (1.5%)	0.008
CVD - Coronary atherosclerosis and other forms of chronic ischemic heart disease; n (%)	2,082 (11.6%) 512 (2.8%)	2,082 (11.6%)	0.0000 -0.0060	3,397 (10.9%) 808 (2.6%)	3,423 (11.0%) 814 (2.6%)	-0.0032 0.0000	5,479 (11.2%) 1,320 (2.7%)	5,505 (11.2%) 1,339 (2.7%)	0.000
CVD - Stroke/TIA; n (%) CVD - Peripheral Vascular Disease (PVD) or PVD Surgery; n (%)	1,333 (7.4%)	525 (2.9%) 1,330 (7.4%)	0.0000	1,482 (4.8%)	814 (2.6%) 1,478 (4.7%)	0.0000	2,815 (5.7%)	2,808 (5.7%)	0.000
CVD - Hyperlipidemia ; n (%)	7.804 (43.3%)	7,866 (43.7%)	-0.0081	8.374 (26.9%)	8,401 (27.0%)	-0.0023	16,178 (32.9%)	16,267 (33.1%)	-0.004
CVD - Hypertension; n (%)	9,269 (51.4%)	9,370 (52.0%)	-0.0120	11,614 (37.3%)	11,709 (37.6%)	-0.0062	20,883 (42.5%)	21,079 (42.9%)	-0.008
- The tament (ta)	5,225 (22.113)	0,010 (02.01.)		==,== : (e-:e-:-)			.,,	, , , , , ,	
CRX - ACEi or ARB; n (%)	6,749 (37.5%)	6,860 (38.1%)	-0.0124	11,265 (36.2%)	11,481 (36.9%)	-0.0145	18,014 (36.7%)	18,341 (37.3%)	-0.012
CRX - Mineralocorticoid receptor antagonist ; n (%)	268 (1.5%)	300 (1.7%)	-0.0159	654 (2.1%)	655 (2.1%)	0.0000	922 (1.9%)	955 (1.9%)	0.000
CRX - Loop or Thiazide diuretics; n (%)	3,888 (21.6%)	3,980 (22.1%)	-0.0121	7,188 (23.1%)	7,276 (23.4%)	-0.0071	11,076 (22.5%)	11,256 (22.9%)	-0.010
CRX - Statins and other lipid lowering agents; n (%)	7,327 (40.7%)	7,417 (41.2%)	-0.0102	12,165 (39.1%)	12,317 (39.6%)	-0.0102	19,492 (39.7%)	19,734 (40.2%)	-0.010
CRX - CCB and other antihypertensives; n (%) CRX - Digoxin : n (%)*	3,956 (22.0%) 279 (1.5%)	4,018 (22.3%) 299 (1.7%)	-0.0072 -0.0159	6,868 (22.1%) 804 (2.6%)	6,911 (22.2%) 874 (2.8%)	-0.0024 -0.0123	10,824 (22.0%)	10,929 (22.2%) 1.173 (2.4%)	-0.005 -0.013
CRX - Digoxin ; n (%)* CRX - Nitrates: n (%)*	279 (1.5%) 585 (3.2%)	299 (1.7%) 585 (3.2%)	0.0000	1,392 (4.5%)	874 (2.8%) 1,445 (4.6%)	-0.0123	1,083 (2.2%)	2,030 (4.1%)	-0.013
Cist (100 Cist) 11 (70)	565 (5.270)	303 (3.270)	5.5000	1,332 (4.370)	1,773 (4.070)	5.0040	2,5 (4.0/0)	2,000 (4.170)	3.003
OCM - Type 1 or 2 DM; n (%)	3,731 (20.7%)	3,818 (21.2%)	-0.0123	5,268 (16.9%)	5,288 (17.0%)	-0.0027	8,999 (18.3%)	9,106 (18.5%)	-0.005
OCM - Occurrence of Diabetic retinopathy/nephropathy/neuropathy; n (%)*	1,023 (5.7%)	1,174 (6.5%)	-0.0334	914 (2.9%)	942 (3.0%)	-0.0059	1,937 (3.9%)	2,116 (4.3%)	-0.020
OCM - Hypertensive nephropathy; n (%)*	557 (3.1%)	600 (3.3%)	-0.0114	379 (1.2%)	377 (1.2%)	0.0000	936 (1.9%)	977 (2.0%)	-0.007
OCM-Hypotension ; n (%)*	300 (1.7%)	292 (1.6%)	0.0079	389 (1.2%)	353 (1.1%)	0.0094	689 (1.4%)	645 (1.3%)	0.009
OCM - Hyperkalemia ; n (%)*	170 (0.9%)	191 (1.1%)	-0.0201	185 (0.6%)	170 (0.5%)	0.0135	355 (0.7%)	361 (0.7%)	0.000
OCM - CKD II, III, or IV; n (%)	994 (5.5%)	1,011 (5.6%)	-0.0044 0.0000	565 (1.8%)	578 (1.9%)	-0.0074	1,559 (3.2%) 189 (0.4%)	1,589 (3.2%)	0.000
OCM - HD/PD/ESRD; n (%)* OCM - Osteoporosis; n (%)	60 (0.3%)	63 (0.3%) 2,099 (11.7%)	0.0000	129 (0.4%) 3,085 (9.9%)	161 (0.5%) 3,127 (10.0%)	-0.0149 -0.0033	5,190 (10.6%)	224 (0.5%) 5,226 (10.6%)	-0.015 0.000
OCM - Osteoporosis; II (%) OCM - Sleep apnea; n (%)	1.533 (8.5%)	1,510 (8.4%)	0.0036	2,639 (8.5%)	2.612 (8.4%)	0.0036	4,172 (8.5%)	4,122 (8.4%)	0.004
OCM-Fractures : n (%)	792 (4.4%)	795 (4.4%)	0.0000	1,410 (4.5%)	1,453 (4.7%)	-0.0095	2.202 (4.5%)	2,248 (4.6%)	-0.005
OCM - Other Arthritis, Arthropathies and Musculoskeletal Pain ; n (%)	6,547 (36.3%)	6,597 (36.6%)	-0.0062	9,534 (30.6%)	9,658 (31.0%)	-0.0087	16,081 (32.7%)	16,255 (33.1%)	-0.009
OCM - Dorsopathies; n (%)	5,053 (28.0%)	5,104 (28.3%)	-0.0067	7,003 (22.5%)	7,086 (22.8%)	-0.0072	12,056 (24.5%)	12,190 (24.8%)	-0.007
OCM - Gout (acute/chronic) ; n (%)*	121 (0.7%)	143 (0.8%)	-0.0116	238 (0.8%)	227 (0.7%)	0.0116	359 (0.7%)	370 (0.8%)	-0.012
OCM-Hyperthyroidism ; n (%)*	121 (0.7%)	107 (0.6%)	0.0124	145 (0.5%)	142 (0.5%)	0.0000	266 (0.5%)	249 (0.5%)	0.000
OCM - Hypothyroidism ; n (%)*	1,760 (9.8%)	1,783 (9.9%)	-0.0034	2,214 (7.1%)	2,255 (7.2%)	-0.0039	3,974 (8.1%)	4,038 (8.2%)	-0.004
OCM - VTE; n (%)*	333 (1.8%)	337 (1.9%)	-0.0074	570 (1.8%)	583 (1.9%)	-0.0074	903 (1.8%)	920 (1.9%) 4,881 (9.9%)	-0.007 0.003
OCM - GERD ; n (%) OCM - Cancer ; n (%)	2,541 (14.1%) 1.869 (10.4%)	2,518 (14.0%) 1,909 (10.6%)	0.0029 -0.0065	2,368 (7.6%) 2,579 (8.3%)	2,363 (7.6%) 2,626 (8.4%)	0.0000 -0.0036	4,909 (10.0%) 4,448 (9.1%)	4,535 (9.2%)	-0.003
OCM - Hypovolemia/volume depletion ; n (%)*	383 (2.1%)	404 (2.2%)	-0.0069	523 (1.7%)	558 (1.8%)	-0.0076	906 (1.8%)	962 (2.0%)	-0.015
OCM-Anemia ; n (%)	1,830 (10.2%)	1,853 (10.3%)	-0.0033	2,414 (7.8%)	2,460 (7.9%)	-0.0037	4,244 (8.6%)	4,313 (8.8%)	-0.007
OCM-Dementia ; n (%)*	639 (3.5%)	763 (4.2%)	-0.0364	751 (2.4%)	916 (2.9%)	-0.0311	1,390 (2.8%)	1,679 (3.4%)	-0.035
OCM - Depression ; n (%)	2,800 (15.5%)	2,815 (15.6%)	-0.0028	2,980 (9.6%)	2,938 (9.4%)	0.0068	5,780 (11.8%)	5,753 (11.7%)	0.003
ORX - Metformin; n (%)*	1,839 (10.2%)	1,854 (10.3%)	-0.0033	2,684 (8.6%)	2,719 (8.7%)	-0.0036	4,523 (9.2%)	4,573 (9.3%)	-0.003
ORX -1st and 2nd Generation SUs ; n (%)	896 (5.0%) 755 (4.2%)	922 (5.1%) 776 (4.3%)	-0.0046 -0.0050	1,594 (5.1%) 1,328 (4.3%)	1,545 (5.0%) 1,333 (4.3%)	0.0046	2,490 (5.1%) 2,083 (4.2%)	2,467 (5.0%) 2,109 (4.3%)	0.005 -0.005
ORX - Insulins ; n (%) ORX - Other antidiabetic medications use; n (%)	755 (4.2%) 683 (3.8%)	7/6 (4.3%) 662 (3.7%)	0.0053	1,328 (4.3%)	1,333 (4.3%)	0.0000	2,169 (4.4%)	2,109 (4.3%)	0.000
ORX - Other antidiabetic medications use; if (%) ORX - PPIs or H2RAs use; n (%)*	4,194 (23.3%)	4,378 (24.3%)	-0.0235	6,598 (21.2%)	6,855 (22.0%)	-0.0194	10,792 (22.0%)	11,233 (22.9%)	-0.022
ORX - NSAIDs ; n (%)*	2,930 (16.3%)	3,002 (16.7%)	-0.0108	5,255 (16.9%)	5,441 (17.5%)	-0.0159	8,185 (16.7%)	8,443 (17.2%)	-0.013
ORX - Use of opioids ; n (%)*	6,320 (35.1%)	6,310 (35.0%)	0.0021	11,650 (37.4%)	11,206 (36.0%)	0.0290	17,970 (36.6%)	17,516 (35.6%)	0.021
ORX - Use of antipsychotics ; n (%)*	815 (4.5%)	809 (4.5%)	0.0000	1,220 (3.9%)	1,219 (3.9%)	0.0000	2,035 (4.1%)	2,028 (4.1%)	0.000
ORX - Use of antidepressants ; n (%)	6,448 (35.8%)	6,479 (36.0%)	-0.0042	10,791 (34.7%)	10,840 (34.8%)	-0.0021	17,239 (35.1%)	17,319 (35.2%)	-0.002
ORX - Use of anxiolytics/hypnotics ; n (%)	1,758 (9.8%)	1,771 (9.8%)	0.0000	3,350 (10.8%)	3,360 (10.8%)	0.0000	5,108 (10.4%)	5,131 (10.4%)	0.000
ORX - Use of Panadianania or a 19(4)*	3,002 (16.7%)	2,999 (16.6%) 2,933 (16.3%)	0.0027 0.0161	4,192 (13.5%)	4,186 (13.5%)	0.0000 0.0241	7,194 (14.6%) 10.109 (20.6%)	7,185 (14.6%) 9,694 (19.7%)	0.000
ORX - Use of Benzodiazepines ; n (%)* ORX - Use of dementia meds ; n (%)*	3,043 (16.9%) 451 (2.5%)	2,933 (16.3%) 528 (2.9%)	-0.0247	7,066 (22.7%) 744 (2.4%)	6,761 (21.7%) 906 (2.9%)	-0.0311	1,195 (2.4%)	1,434 (2.9%)	-0.031
ORX - Use of antiparkinsonian meds ; n (%)*	686 (3.8%)	657 (3.6%)	0.0106	1,028 (3.3%)	1,055 (3.4%)	-0.0056	1,714 (3.5%)	1,712 (3.5%)	0.000
ORX - Use of oral anticoagulants ; n (%)*	879 (4.9%)	891 (4.9%)	0.0000	1,774 (5.7%)	1,819 (5.8%)	-0.0043	2,653 (5.4%)	2,710 (5.5%)	-0.004
ORX - Use of antiplatelet agents ; n (%)*	1,174 (6.5%)	1,104 (6.1%)	0.0165	3,085 (9.9%)	2,922 (9.4%)	0.0169	4,259 (8.7%)	4,026 (8.2%)	0.018
				, ,					
LFS - Obesity; n (%)	1,298 (7.2%)	1,310 (7.3%)	-0.0039	1,289 (4.1%)	1,290 (4.1%)	0.0000	2,587 (5.3%)	2,600 (5.3%)	0.000
PFT - Spirometry test only; n (%)	3,180 (17.6%)	3,028 (16.8%)	0.0212	7,080 (22.7%)	6,932 (22.3%)	0.0096	10,260 (20.9%)	9,960 (20.3%)	0.015
PFT - Spirometry test only (Count - 180 days to 31 days before CED) *mean (sd)	0.18 (0.66)	0.18 (0.65)	0.0000	0.20 (0.64)	0.22 (0.65)	-0.0310	0.19 (0.65)	0.21 (0.65)	-0.031
median [IQR]	0.00 [0.00, 0.00]	0.00 [0.00, 0.00]	0.0000	0.00 [0.00, 0.00]	0.00 [0.00, 0.00]	0.0000	0.00 (0.65)	0.00 (0.65)	0.000
PFT - Spirometry test only (Count - 30 days to CED) *									

mean (sd)	0.14 (0.56)	0.11 (0.48)	0.0575	0.17 (0.55)	0.13 (0.47)	0.0782	0.16 (0.55)	0.12 (0.47)	0.078
median [IQR]	0.00 [0.00, 0.00]	0.00 [0.00, 0.00]	0.0000	0.00 [0.00, 0.00]	0.00 [0.00, 0.00]	0.0000	0.00 (0.55)	0.00 (0.47)	0.000
PFT - Lung volume, Diffuse capacity, pulmonary stress testing (any); n (%)	1,987 (11.0%)	1,910 (10.6%)	0.0129	3,084 (9.9%)	2,970 (9.5%)	0.0135	5,071 (10.3%)	4,880 (9.9%)	0.013
g in g	, , , , , , , , , , , , , , , , , , , ,	, , , , , , , , , , , , , , , , , , , ,		γ ,	, , , , ,				
HCU - Pulmonologist visit (180 to 1 day before CED); n (%)	189 (1.0%)	182 (1.0%)	0.0000	5,646 (18.1%)	5,482 (17.6%)	0.0131	5,835 (11.9%)	5,664 (11.5%)	0.012
HCU - Pulmonologist visit on CED; n (%)	24 (0.1%)	24 (0.1%)	0.0000	949 (3.0%)	932 (3.0%)	0.0000	973 (2.0%)	956 (1.9%)	0.007
HCU - Pulmonologist visit (Number of during CAP) *	' '	` '		· ·	` '				
mean (sd)	0.06 (0.94)	0.07 (0.94)	-0.0106	0.75 (2.21)	0.70 (2.11)	0.0231	0.50 (1.85)	0.47 (1.77)	0.017
median [IQR]	0.00 [0.00, 0.00]	0.00 [0.00, 0.00]	0.0000	0.00 [0.00, 0.00]	0.00 [0.00, 0.00]	0.0000	0.00 (1.85)	0.00 (1.77)	0.000
HCU - Number of Internal Medicine/Family Medicine Visits									
mean (sd)	7.48 (11.28)	7.62 (11.09)	-0.0125	6.14 (9.32)	6.16 (9.74)	-0.0021	6.63 (10.08)	6.70 (10.26)	-0.007
median [IQR]	4.00 [1.00, 10.00]	4.00 [1.00, 10.00]	0.0000	4.00 [1.00, 8.00]	3.00 [1.00, 8.00]	0.1049	4.00 (10.08)	3.37 (10.26)	0.062
HCU - Number of Cardiologist visits									
mean (sd)	0.86 (3.19)	0.86 (2.82)	0.0000	0.79 (2.82)	0.79 (3.36)	0.0000	0.82 (2.96)	0.82 (3.17)	0.000
median [IQR]	0.00 [0.00, 0.00]	0.00 [0.00, 0.00]	0.0000	0.00 [0.00, 0.00]	0.00 [0.00, 0.00]	0.0000	0.00 (2.96)	0.00 (3.17)	0.000
HCU - Number of Emergency Department (ED) visits v3									
mean (sd)	0.46 (1.29)	0.47 (1.25)	-0.0079	0.17 (1.12)	0.16 (0.95)	0.0096	0.28 (1.19)	0.27 (1.07)	0.009
median [IQR]	0.00 [0.00, 0.00]	0.00 [0.00, 0.00]	0.0000	0.00 [0.00, 0.00]	0.00 [0.00, 0.00]	0.0000	0.00 (1.19)	0.00 (1.07)	0.000
HCU - Old hospitalization (-180 days to -31 days before CED); n (%)	1,508 (8.4%)	1,514 (8.4%)	0.0000	4,137 (13.3%)	4,095 (13.2%)	0.0029	5,645 (11.5%)	5,609 (11.4%)	0.003
HCU - Recent hospitalization (-30 days to CED date); n (%)	166 (0.9%)	166 (0.9%)	0.0000	532 (1.7%)	523 (1.7%)	0.0000	698 (1.4%)	689 (1.4%)	0.000
HCU - Number of hospitalizations during CAP									
mean (sd)	0.11 (0.37)	0.11 (0.37)	0.0000	0.17 (0.43)	0.16 (0.43)	0.0233	0.15 (0.41)	0.14 (0.41)	0.024
median [IQR]	0.00 [0.00, 0.00]	0.00 [0.00, 0.00]	0.0000	0.00 [0.00, 0.00]	0.00 [0.00, 0.00]	0.0000	0.00 (0.41)	0.00 (0.41)	0.000
HCU - Blood eosinophilia or Serum IgE test order; n (%)*	85 (0.5%)	93 (0.5%)	0.0000	113 (0.4%)	136 (0.4%)	0.0000	198 (0.4%)	229 (0.5%)	-0.015
HCU - Pneumococcal vaccine; n (%)	2,119 (11.8%)	2,112 (11.7%)	0.0031	1,615 (5.2%)	1,601 (5.1%)	0.0045	3,734 (7.6%)	3,713 (7.6%)	0.000
HCU - Flu vaccine ; n (%)	3,385 (18.8%)	3,370 (18.7%)	0.0026	3,684 (11.8%)	3,659 (11.8%)	0.0000	7,069 (14.4%)	7,029 (14.3%)	0.003
HCU - Bone mineral density ; n (%)	795 (4.4%)	788 (4.4%)	0.0000	931 (3.0%)	953 (3.1%)	-0.0058	1,726 (3.5%)	1,741 (3.5%)	0.000
HCU - Pap smear; n (%)	711 (3.9%)	707 (3.9%)	0.0000	1,429 (4.6%)	1,419 (4.6%)	0.0000	2,140 (4.4%)	2,126 (4.3%)	0.005
HCU - Mammogram ; n (%)	2,274 (12.6%)	2,273 (12.6%)	0.0000	3,319 (10.7%)	3,340 (10.7%)	0.0000	5,593 (11.4%)	5,613 (11.4%)	0.000
HCU - Prostate exam for DRE; n (%)	542 (3.0%)	545 (3.0%)	0.0000	517 (1.7%)	509 (1.6%)	0.0079	1,059 (2.2%)	1,054 (2.1%)	0.007
HCU - Number of Echocardiogram *									
mean (sd)	0.20 (1.27)	0.19 (1.21)	0.0081	0.23 (0.80)	0.23 (0.84)	0.0000	0.22 (1.00)	0.22 (0.99)	0.000
median [IQR]	0.00 [0.00, 0.00]	0.00 [0.00, 0.00]	0.0000	0.00 [0.00, 0.00]	0.00 [0.00, 0.00]	0.0000	0.00 (1.00)	0.00 (0.99)	0.000
HCU - Flexible Sigmoidoscopy or colonoscopy or CT virtual colonoscopy ; n (%)	816 (4.5%)	808 (4.5%)	0.0000	1,609 (5.2%)	1,634 (5.3%)	-0.0045	2,425 (4.9%)	2,442 (5.0%)	-0.005
HCU - Number of Distinct Medication Prescriptions (not generalized to generics)									
mean (sd)	20.27 (17.04)	20.34 (16.67)	-0.0042	19.34 (15.01)	19.39 (15.01)	-0.0033	19.68 (15.78)	19.74 (15.64)	-0.004
median [IQR]	16.00 [8.00, 27.00]	16.00 [9.00, 27.00]	0.0000	16.00 [9.00, 26.00]	16.00 [9.00, 26.00]	0.0000	16.00 (15.78)	16.00 (15.64)	0.000
SES - Copay for pharmacy cost (charges in U.S. \$)									
mean (sd)	32.00 (38.05)	31.87 (35.15)	0.0035	25.66 (26.01)	25.75 (26.16)	-0.0035	27.98 (30.97)	27.99 (29.77)	0.000
median [IQR]	23.60 [10.60, 40.25]	24.23 [10.04, 41.52]	-0.0172	20.26 [10.00, 34.37]	20.61 [9.80, 34.59]	-0.0134	21.48 (30.97)	21.94 (29.77)	-0.015
SES - Business type									
Commercial; n (%)	5,963 (33.1%)	5,735 (31.8%)	0.0278				5,963 (33.1%)	5,735 (31.8%)	0.028
Medicare; n (%)	12,054 (66.9%)	12,282 (68.2%)	-0.0278			\perp	12,054 (66.9%)	12,282 (68.2%)	-0.028
SES - Low income indicator ; n (%)	3,483 (19.3%)	3,604 (20.0%)	-0.0176			\perp	3,483 (19.3%)	3,604 (20.0%)	-0.018
SES - Insurance Plan type									
Comprehensive; n (%)				9,074 (29.2%)	9,146 (29.4%)	-0.0044	9,074 (29.2%)	9,146 (29.4%)	-0.004
HMO; n (%)				3,810 (12.2%)	3,763 (12.1%)	0.0031	3,810 (12.2%)	3,763 (12.1%)	0.003
PPO; n (%)				14,372 (46.2%)	14,423 (46.3%)	-0.0020	14,372 (46.2%)	14,423 (46.3%)	-0.002
Others; n (%)				3,866 (12.4%)	3,790 (12.2%)	0.0061	3,866 (12.4%)	3,790 (12.2%)	0.006

^{*} Not included in PS model

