1.1 Title

The Prevention of Chronic Obstructive Pulmonary Disease Exacerbations by Salmeterol/Fluticasone Propionate or Tiotropium Bromide (INSPIRE trial)

1.2 Intended aim(s)

The objective of the study is to compare the effect of the anti-inflammatory/bronchodilator combination of salmeterol/fluticasone propionate (SFC) with the bronchodilator tiotropium bromide on the rate of moderate and/or severe exacerbations during a 2-year treatment period, and secondarily on outcomes that might relate to exacerbations.

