Initiators of tiotropium inhaler defined as no use of inhaled tiotropium during the 180 days prior to index date

Patients are required to be incident users with respect to both exposure groups.

6.2 Preliminary Covariates:

- Age
- Sex
- Combined Comorbidity Index (CCI), measured over the default baseline covariate assessment period of 180 days prior to and including the index prescription date

Covariates listed above are a small subset of covariates that will ultimately be controlled in the design and analysis phase of the study. They are included in the preliminary assessment to determine the presence of adequate overlap between the two population of patients to proceed to the next phase of the study. Remaining covariates are defined only after the study has passed the initial feasibility analysis and initial power assessment and are listed in Table 1 (Appendix B).

6.3 Outcome variables and study follow-up:

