6.3.2 Study follow-up

Both as-treated (AT) and intention-to-treat (ITT) analysis will be conducted with treatment defined as the index drug on the day of cohort entry. Because adherence in the real-world databases is expected to be much worse than in the trial, the AT analysis is the **primary** analysis, as it targets the relative rate of outcomes on treatment.

For the AT analysis, the follow-up will start the day after the initiation of SFC or tiotropium and will continue until the earliest date of the following events:

- The date of end of continued registration in the database,
- End of the study period or 730 days after cohort entry date,
- Death,
- Nursing home admission
 - Nursing home admissions are considered a censoring event because the data sources utilized typically
 provide little to no data on a patient, particularly on drug utilization, after admission. We will utilize this
 as an exclusion reason for cohorts for the same reason.
- The date of drug discontinuation, defined as the date of the last continuous treatment episode of the index drug (SFC or tiotropium) + a 60-day grace period,
- The date of switching from an exposure to comparator and vice versa,
- The date of switching to or initiation of other LAMA (excluding tiotropium) and switch or initiation to other LABA/ICS (excluding SFC), LAMA/LABA, LABA only, LAMA/LABA/ICS combination, and ICS only inhalers.

For the ITT analyses, the censoring based on the switching and treatment discontinuation will be replaced with a maximum allowed follow-up time of 365 days.

7 Initial Feasibility Analysis

Aetion report name:

Optum- https://bwh-dope.aetion.com/projects/details/1742/rwrs/71660
Marketscan- https://bwh-dope.aetion.com/projects/details/1741/rwrs/71658

Date conducted: 6/17/2021

Complete Aetion feasibility analysis using age, sex, and CCI as the only covariates and the primary endpoint (Section 6.3.1) as the outcome. No measures of association will be computed nor will incidence rates stratified by treatment group.

8 Initial Power Assessment

Aetion report name:

Optum- https://bwh-dope.aetion.com/projects/details/1742/rwrs/71659
Marketscan- https://bwh-dope.aetion.com/projects/details/1741/rwrs/71657

Date conducted: 6/17/2021

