In order to complete the initial power analysis, the dummy outcome of a 90-day gap in database enrollment will be used. Complete a 1:1 PS-matched comparative analysis using this outcome. PS should include only 3 covariates: age, sex, and combined comorbidity index.

- Stop analyses until feasibility and power are reviewed by primary investigators and FDA. Reviewers evaluate the results of the analyses described above in Sections 7 and 8, including numbers of patients, patient characteristics, follow-up time, and reasons for censoring by treatment group, as well as overall rates of outcomes and study power. These parameters are re-evaluated and reported in the subsequent sections, after incorporating feedback and refining the protocol.
- Stop analyses until feasibility and power are reviewed by primary investigators, FDA, and assigned members of advisory board.

Reviewed by PI:	[name]	Date reviewed:	
Reviewed by FDA:	[name]	Date reviewed:	
Reasons for stopping			
analysis (if required):			

Effectiveness research with Real World Data to support FDA's regulatory decision making

9. Balance Assessment

Optum- https://bwh-dope.aetion.com/projects/details/1742/rwrs/72363
Marketscan- https://bwh-dope.aetion.com/projects/details/1741/rwrs/72364

Date conducted: 7/14/2021

After review of initial feasibility and power analyses, complete creation of the remaining covariates from Section 6.2. Again, using the dummy outcome of a 90-day gap in database enrollment, complete a 1:1 PS-matched analysis. The PS should include the complete list of covariates.

• Provide plot of PS distributions stratified by treatment group.

Note- Please refer to Appendix B.

• Report covariate balance after matching.

Note- For Table 1, please refer to Appendix B.

• Report reasons for censoring by treatment group.

	Overall	Referent	Exposure
Dummy outcome	0 (0%)	0 (0%)	0 (0%)
Death	706 (0.72%)	368 (0.75%)	338 (0.69%)
Start of an additional exposure	8,037 (8.18%)	4,562 (9.28%)	3,475 (7.07%)
End of Index Exposure	63,915 (65.03%)	29,311 (59.65%)	34,604 (70.42%)
Specified date reached	2,286 (2.33%)	1,069 (2.18%)	1,217 (2.48%)
End of patient enrollment	11,722 (11.93%)	5,877 (11.96%)	5,845 (11.89%)
Switch to other LABA, LAMA + LABA/LAMA combo + LAMA/LABA/ICS combo + ICS only + NH admissions Occurred	11,612 (11.82%)	7,952 (16.18%)	3,660 (7.45%)

• Report follow-up time by treatment group.

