PRX - Antibiotics treatment (30 days to CED); n (%)	3,096 (14.3%) 6.911 (31.9%)	5,872 (19.2%)	-0.1315 -0.0107	6,246 (17.0%)	14,851 (23.0%) 20.935 (32.4%)	-0.1504	9,342 (16.0%) 18,504 (31.7%)	20,723 (21.8%) 30,848 (32.4%)	-0.149 -0.015
PRX - Systemic Corticosteroids (with CPT) (180 days to 31 days before CED); n (%) PRX - Systemic Corticosteroids (with CPT) (30 days to CED); n (%)	1,106 (5.1%)	9,913 (32.4%) 3,126 (10.2%)	-0.0107	11,593 (31.6%) 2,576 (7.0%)	8,168 (12.6%)	-0.0172	3,682 (6.3%)	11,294 (11.9%)	-0.015
PRX - Roflumilast; n (%)	67 (0.3%)	42 (0.1%)	0.0448	162 (0.4%)	76 (0.1%)	0.0601	229 (0.4%)	118 (0.1%)	0.060
PRX - ROHUHHIIdSC, II (%)	67 (0.3%)	42 (0.1%)	0.0448	182 (0.4%)	76 (0.1%)	0.0001	223 (0.470)	110 (0.170)	0.000
CVD - Unstable angina/MI; n (%)	593 (2.7%)	643 (2.1%)	0.0392	701 (1.9%)	1,029 (1.6%)	0.0229	1,294 (2.2%)	1,672 (1.8%)	0.029
CVD - Stable Angina ; n (%)	403 (1.9%)	486 (1.6%)	0.0229	573 (1.6%)	834 (1.3%)	0.0251	976 (1.7%)	1,320 (1.4%)	0.024
CVD - Any Heart failure (HF) ; n (%)	1,334 (6.2%)	1,649 (5.4%)	0.0342	2,076 (5.7%)	3,132 (4.8%)	0.0404	3,410 (5.8%)	4,781 (5.0%)	0.035
CVD - Atrial fibrillation; n (%)	1,091 (5.0%)	1,261 (4.1%)	0.0432	1,764 (4.8%)	2,458 (3.8%)	0.0493	2,855 (4.9%)	3,719 (3.9%)	0.049
CVD - Other dysrythmias ; n (%)*	1,576 (7.3%)	1,894 (6.2%)	0.0439	2,195 (6.0%)	3,210 (5.0%)	0.0439	3,771 (6.5%)	5,104 (5.4%)	0.047
CVD - Valve disorder ; n (%)	277 (1.3%)	332 (1.1%)	0.0184	336 (0.9%)	612 (0.9%)	0.0000	613 (1.0%)	944 (1.0%)	0.000
CVD - Implantable cardioverter defibrillator ; n (%)*	69 (0.3%)	82 (0.3%)	0.0000	111 (0.3%)	109 (0.2%)	0.0200	180 (0.3%)	191 (0.2%)	0.020
CVD - CABG/PCI; n (%)	521 (2.4%)	534 (1.7%)	0.0494	464 (1.3%)	595 (0.9%)	0.0384	985 (1.7%)	1,129 (1.2%)	0.042
CVD - Coronary atherosclerosis and other forms of chronic ischemic heart disease; n (%)	2,581 (11.9%)	2,968 (9.7%)	0.0709	4,121 (11.2%)	5,577 (8.6%)	0.0871	6,702 (11.5%)	8,545 (9.0%)	0.082
CVD - Stroke/TIA ; n (%)	641 (3.0%)	713 (2.3%)	0.0436	943 (2.6%)	1,546 (2.4%)	0.0128	1,584 (2.7%)	2,259 (2.4%)	0.019
CVD - Peripheral Vascular Disease (PVD) or PVD Surgery; n (%)	1,693 (7.8%)	1,661 (5.4%)	0.0968	1,776 (4.8%)	2,384 (3.7%)	0.0545	3,469 (5.9%)	4,045 (4.2%)	0.078
CVD - Hyperlipidemia ; n (%)	9,573 (44.1%)	12,176 (39.8%)	0.0872	10,218 (27.8%)	15,419 (23.8%)	0.0915	19,791 (33.9%)	27,595 (29.0%)	0.106
CVD - Hypertension; n (%)	11,323 (52.2%)	14,593 (47.7%)	0.0901	13,871 (37.8%)	21,783 (33.7%)	0.0856	25,194 (43.1%)	36,376 (38.2%)	0.100

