SES - Low income indicator ; n (%)	4,586 (21.1%)	4,970 (16.3%)	0.1233			+	4,586 (21.1%)	4,970 (16.3%)	0.123
SES - Insurance Plan type		+	+	10,656 (29.0%)	16,804 (26.0%)	0.0672	10,656 (29.0%)	16 904 (26 000)	0.067
Comprehensive; n (%)		+	+			-0.0303		16,804 (26.0%)	-0.030
HMO; n (%)			+ +	4,376 (11.9%)	8,310 (12.9%)		4,376 (11.9%)	8,310 (12.9%)	
PPO; n (%)			+ +	17,092 (46.5%)	30,849 (47.7%)	-0.0240	17,092 (46.5%)	30,849 (47.7%)	-0.024 -0.027
Others; n (%)		l	1 1	4,603 (12.5%)	8,690 (13.4%)	-0.0268	4,603 (12.5%)	8,690 (13.4%)	-0.027

^{*} Not included in PS model

PS MATCHED	OPTUM			-	MARKETSCAN	POOLED			
Number of patients	Referent - Tiotropium 18,017	Exposure - Salmeterol/Fluticasone 18,017	St. Diff	Referent - Tiotropium 31,122	Exposure - Salmeterol/Fluticasone 31,122	St. Diff	Referent - Tiotropium 49,139	Exposure - Salmeterol/Fluticasone 49,139	e St. Diff
Calendar Time - Year of Initiation (2004 - 2020)	18,017	18,017		31,122	31,122		49,139	49,139	+
2004-2006; n (%)	1,289 (7.2%)	1,219 (6.8%)	0.0157	5,326 (17.1%)	5,292 (17.0%)	0.0027	6,615 (13.5%)	6,511 (13.3%)	0.006
2007-2008; n (%)	2,030 (11.3%)	2,065 (11.5%)	-0.0063	5,203 (16.7%)	5,279 (17.0%)	-0.0080	7,233 (14.7%)	7,344 (14.9%)	-0.006
2009-2011; n (%)	3,594 (19.9%)	3,602 (20.0%)	-0.0025	8,529 (27.4%)	8,599 (27.6%)	-0.0045	12,123 (24.7%)	12,201 (24.8%)	-0.002
2012-2015; n (%)	5,440 (30.2%)	5,414 (30.0%)	0.0044	9,009 (28.9%)	8,912 (28.6%)	0.0066	14,449 (29.4%)	14,326 (29.2%)	0.004
2016-2018; n (%)	3,880 (21.5%)	3,887 (21.6%)	-0.0024	3,055 (9.8%)	3,040 (9.8%)	0.0000	6,935 (14.1%)	6,927 (14.1%)	0.000
2019-Mar. 2020; n (%)	1,784 (9.9%)	1,830 (10.2%)	-0.0100				1,784 (9.9%)	1,830 (10.2%)	-0.010
DMG - Age									+
mean (sd)	67.43 (10.50)	67.84 (11.57)	-0.0371	65.64 (11.34)	66.01 (12.78)	-0.0306	66.30 (11.04)	66.68 (12.35)	-0.032
median [IQR]	68.00 [60.00, 75.00]	69.00 [60.00, 76.00]	-0.0905	64.00 [58.00, 74.00]	65.00 [57.00, 76.00]	-0.0828	65.47 (11.04)	66.47 (12.35)	-0.085
DMG - Gender							10.000 (00.00)		
Male; n (%)	6,330 (35.1%)	6,304 (35.0%)	0.0021	12,025 (38.6%)	12,000 (38.6%)	0.0000	18,355 (37.4%)	18,304 (37.2%)	0.004
Female; n (%) DMG - Geographic region	11,687 (64.9%)	11,713 (65.0%)	-0.0021	19,097 (61.4%)	19,122 (61.4%)	0.0000	30,784 (62.6%)	30,835 (62.8%)	-0.004
Northeast: n (%)	1,731 (9.6%)	1,705 (9.5%)	0.0034	4,713 (15.1%)	4,752 (15.3%)	-0.0056	6,444 (13.1%)	6,457 (13.1%)	0.000

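### Season of cohort entry is neither in the propensity score nor in the balance table, although median as-treated follow-up is only 88 to 113 days

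*Combined protocol and SAP*

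**What the plan says.** Section 6.2 starts with age, sex and the comorbidity index. It says that the remaining covariates are defined after the "initial feasibility analysis and initial power assessment and are listed in Table 1 (Appendix B"). Section 9 then instructs: "The PS should include the complete list of covariates". In Table 1, before and after matching, the one calendar entry is "Calendar Time - Year of Initiation (2004 - 2020"), split into 2004-2006, 2007-2008, 2009-2011, 2012-2015, 2016-2018 and 2019 to March 2020. Several rows carry an asterisk, meaning that they are reported but not in the model. None of these, and no unstarred row, is month, quarter or season of entry. No stratified or sensitivity analysis by season is described.

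The as-treated analysis is primary (Section 6.3.2), "as it targets the relative rate of outcomes on treatment". Follow-up stops at switching or at discontinuation plus "a 60-day grace period", among other events. Section 9 reports the resulting follow-up, median [IQR]: 88 [88, 162] days in Optum and 113 [88, 180] days in MarketScan. The ITT analysis drops these two censoring rules in favour of "a maximum allowed follow-up time of 365 days". Section 1.2 describes the emulated trial as comparing treatments "on the rate of moderate and/or severe exacerbations during a 2-year treatment period".

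**The concern.** Over two years of randomised follow-up, every patient passes through each season about equally, and the arms are comparable in start date by design. The emulation has neither protection in its primary analysis. If exacerbations are seasonal, and if one drug is started more often ahead of or during the high-risk season, then season of entry is related to both treatment and outcome.

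A difference in start pattern is plausible before matching. For "PRX - Systemic Corticosteroids (with CPT) (30 days to CED); n" (%) in the unmatched Table 1, SFC starters have 11.9% (11,294/95,223) against 6.3% (3,682/58,416) for tiotropium. For antibiotics in the same window the figures are 21.8% and 16.0%. Both suggest that SFC is started more often around an acute respiratory episode.

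The index date is held for every patient, so this is a measured variable left unused. With about 14,100 expected events, sampling error is small enough that a shift of one or two percent is not lost in noise. A larger sample would not remove it.

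**Working it through.** **1. The plan's own figure.** Section 10, pooled: (49,138 + 49,139) × 143.63/1,000 = 98,277 × 0.14363 = 14,115.5 events, as stated. The approximate standard error of the log ratio is 2/√14,115.5 = 0.0168. The 95% CI half-width is exp(1.96 × 0.0168) − 1 = 3.4%.

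**2. How far the start date fixes winter exposure.** Assumptions: start dates spread evenly over the year, winter is December to February (90 days), and follow-up begins the day after entry (Section 6.3.2).

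| Follow-up (days) | Source | Start dates with any winter time | Winter share of follow-up, lowest to highest |
|---|---|---|---|
| 88 | Optum median | 49% | 0% to 100% |
| 113 | MarketScan median | 55% | 0% to 80% |
| 162 | Optum upper quartile | 69% | 0% to 56% |
| 180 | MarketScan upper quartile | 74% | 0% to 50% |
| 365 | ITT cap | 100% | 25% for every start date |

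**3. From excess starts to excess winter person-time.** Follow-up runs past the season in which it began, so an excess of d in winter starts is not an excess of d in winter person-time. It shifts the winter share by f × d, where f is the mean winter share among those starting in the block minus the mean among all others.

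- Starts in December to February, 88 days: 50.6% − 16.2%, f = 0.34.
- Starts in December to February, 113 days: 39.4% − 19.8%, f = 0.20.
- The 91-day start block with most winter exposure, 88 days (block opens mid-October): 75.3% − 7.8%, f = 0.67.
- The same, 113 days (block opens early October): 68.4% − 10.1%, f = 0.58.

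**4. Bias in the rate ratio.** With R the winter to non-winter rate ratio and a base winter share of 0.25:

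bias = [1 + (R − 1)(0.25 + f·d)] / [1 + (R − 1)(0.25)]

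R (1.3 to 2.0), the 25% base share and d = 0.05 are assumptions; the documents give none of them. Example: R = 2, f = 0.344, f·d = 0.0172, bias = 1.2672/1.25 = 1.014.

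| 5-point excess of starts in | Follow-up (days) | R = 1.3 | R = 2.0 |
|---|---|---|---|
| December to February | 88 | 0.5% | 1.4% |
| December to February | 113 | 0.3% | 0.8% |
| Block with most winter exposure | 88 | 0.9% | 2.7% |
| Block with most winter exposure | 113 | 0.8% | 2.3% |

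An excess in the tiotropium arm would move the ratio the other way.

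**5. Proxies after matching** (pooled, tiotropium vs SFC): steroids in the 30 days to entry 6.9% vs 6.6%; antibiotics in the same window 16.7% vs 16.4%; flu vaccine 14.4% vs 14.3%; pneumonia 7.0% vs 6.9%.

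**The case against.** The strongest reply is that no link between season and drug is shown. The steroid and antibiotic contrasts are from before matching. They vanish after it, as do flu vaccine (14.8% tiotropium vs 12.8% SFC before matching) and pneumonia. Exclusion 1 also removes anyone with a COPD exacerbation in the 42 days up to and including initiation (33,666 patients in Optum, 34,019 in MarketScan), which limits the acute-illness route to a seasonal difference. All of this stands, and any remaining imbalance must survive conditioning on those variables. It does not settle the matter. About 14% of matched patients have a flu-vaccine code and about 7% recent steroids, so most patients carry no such marker. Balance on the flags is not evidence of balance on the calendar.

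It is also fair that the median understates averaging. A quarter of patients exceed 162 or 180 days, and in a rate analysis they carry more person-time. At those lengths f for winter starts falls to about 0.04 and 0.00, although for the block with most winter exposure it is still 0.40 and 0.34. The 365-day ITT analysis largely averages season for patients who reach the cap, but it is not primary.

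Two stronger readings are tempting. A reader might infer that a 5-point excess of winter starts biases the ratio by up to 4.0% (1.25 becoming 1.30 at R = 2). That treats excess starts as excess winter person-time, which step 3 shows is wrong. A reader might also infer that season could decide whether the result agrees with the trial's 0.967. The documents set no agreement criterion, and the trial's own interval, 0.836 to 1.119, is wide beside a shift of 1% to 3%.

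**Conclusion.** The omission is established: season of entry is absent from the propensity score and from both versions of Table 1, in a primary analysis whose typical follow-up is about three to four months. What follows from it is a possible confounder that has not been checked. The documents do not support saying that the result is biased, because they report neither start dates by arm nor the size of seasonality.

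Under the stated assumptions, a 5-point imbalance is worth about 0.3% to 1.4% for winter starts and 0.8% to 2.7% in the most exposed quarter, in either direction. Both are below the 3.4% half-width, but the upper values are not negligible beside it. These figures take all patients at the median follow-up with evenly spread starts, and the proxies already matched may have removed part of any difference. This is a modest, cheaply removed weakness, mainly in the as-treated analysis.

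**What to change.** Derive calendar quarter of cohort entry from the index date, add it to the propensity score in each database, and re-match. Add its rows by arm to Table 1 before and after matching. Do this before any outcome analysis. Section 10 already stops for review of balance, so the change can be made without knowledge of outcomes by treatment. A 5-point imbalance on a 25% base is a standardised difference of about 0.11, so the new rows would show it.

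Year-by-quarter terms or exact matching on quarter are options, not requirements. The cost is one derived covariate, one re-run of the balance step, and possibly a small change in the number matched, after which the Section 10 counts should be updated.
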